6.6.5.1 CAPOX (Capecitabine/Oxaliplatin)

CAPOX treatment will comprise the following:

- Capecitabine (1000 mg/m², bid for 14 days, Q3W)
- Oxaliplatin (130 mg/m², IV infusion, Q3W)

For capecitabine, older participants are more susceptible to the effects of fluoropyrimidine-based therapies with increased Grade 3/4 adverse effects, especially when used in combination. For oxaliplatin, participants ≥ 65 years have a higher incidence of GI toxicity, myelosuppression, syncope and fatigue. No dose adjustments are needed but caution should be exercised.

Dose modifications for CAPOX are outlined in Table 10 and Table 11.

Table 10 Recommended Dose Modification (Reduction) Guidelines for CAPOX Drug-Related Adverse Events

	Dose Level 0	Dose Level 1	Dose Level 2	Dose Level 3	Dose Level 4
Oxaliplatin (mg/m²)	130	100	75	50	Discontinue
Capecitabine (mg/m ² BID)	1000	750	500	Discontinue	Discontinue

BID=twice daily

MK-7902-015-08 FINAL PROTOCOL 10-JUN-2025

Confidential

Table 11 Recommended Dose Modification Guidelines for CAPOX Drug-Related Adverse Events

Category	Toxicity		Oxaliplatin	Capecitabine
		3 ^b	Hold until neutrophil count resolves to ≥1500/mm ³ No reduction (*consider G-CSF)	Hold until neutrophil count resolves to >1500/mm ³ No dose reduction (consider G-CSF)
	Neutropenia	4 ^b	Hold until neutrophil count resolves to ≥1500/mm ³ Reduce by 1 DL (*recommend G-CSF)	Hold until neutrophil count resolves to >1500/mm³ Reduce by 1 DL (consider G-CSF)
Hematologic	Febrile neutropenia ^a	3 ^b	Hold until neutrophil count resolves to ≥1,500/mm³ • First occurrence: Consider G-CSF • Second occurrence: Dose reduce by 1 DL *recommend G-CSF • Further occurrences: Dose reduce by 2 DL *recommend G-CSF	Hold until toxicity resolves to Grade 0-1 Reduce by 1 DL
		4 ^b D	Discontinue	Discontinue
Thrombocytopenia 1-2 resolves to sirst occurre dose. For fixed dose reductions of the dose		Hold until platelet count resolves to >75,000/mm³. For first occurrence, no change in dose. For further occurrence dose reduce by 1 DL each occurrence.	Hold until platelet count resolves to >75,000/mm³. First occurrence no change in capecitabine dose. For further occurrences dose reduce by 1 DL for each occurrence.	
		3-4 ^b	Hold until platelet count resolves to >75,000/mm ³ Reduce by 1 DL	Hold until platelet count resolves to >75,000/mm³. Reduce by 1 DL

PRODUCT: MK-7902 PROTOCOL/AMENDMENT NO.: 015-08

Category	Toxicity		Oxaliplatin	Capecitabine
	Persistent pares	sthesia	Reduce 1DL	No holding dose. No change in dose
Neurotoxicity	Persistent Paresth pain	esia with	Reduce 2DL or discontinue	No holding dose. No change in dose
	Paresthesia v functional impa		Reduce 2DL if lasting 7-14 days or discontinue if persistent	No holding dose. No change in dose
	Bilirubin 1 to 2 x ULN		No change	Caution
	Bilirubin >2 to 4 x ULN AND/OR AST/ALT 2 to 4 x ULN Bilirubin >4 x ULN AND/OR AST/ALT 4 x ULN No data available ULN		No change	Caution
Hepatic impairment			No data available	OMIT if bilirubin >4 x ULN
	Bilirubin ANY OR AST/ALT >4 x ULN		No data available	OMIT if bilirubin >4 x ULN)
	Creatinine clearance: 50 to 80 mL/min		No change	No dose reduction with close monitoring
Renal impairment	Creatinine clearance: 30 to <50 mL/min		Caution, consider dose reduction	Reduce by 1 DL (use with caution)
	Creatinine clearar mL/min	nce: <30	Discontinue	Discontinue
	Diarrhea, mucositis, or hand-foot syndrome	2-3	Strongly consider discontinuing for diarrhea associated with severe infectious colitis/typhlitis. Reduce by 1DL (or consider discontinue) for diarrhea associated with febrile neutropenia or sepsis.	Hold until toxicity resolves to Grade 0-1 Reduce by 1 DL
Other	-5,	4	Hold until resolves to Grade 1 or 2 Reduce by I DL	Discontinue
	Other toxicities ^c	3-4 ^b	First occurrence: Reduce by 1 DL Second occurrence: Reduce by 2 DL	Hold until toxicity resolves to Grade 0-1 Reduce by 1 DL
	Laboratory adverse events	3-4 ^b	Hold until toxicity resolves to Grade 0-1 Reduce by 1 DL	Hold until toxicity resolves to Grade 0-1 Reduce by 1 DL

Category Toxicity Oxaliplatin Capecitabine	abine
--	-------

DL=dose level; 5-FU=5-fluorouracil; G-CSF=granulocyte colony-stimulating factor; N/A=not applicable.

- ^a May consider restarting when neutrophil count resolves to ≥1000/mm³ per local guidance.
- b Permanent discontinuation should be considered for any severe or life-threatening event and/or if toxicity does not resolve within 4-5 weeks of last administration.
- Participants with intolerable or persistent Grade 2 drug-related adverse event may hold at physician discretion. Permanently discontinue from agent for persistent Grade 2 adverse reactions for which treatment has been held and did not recover to Grades 0-1 within 12 weeks of the last dose.
- *To avoid treatment delays, secondary prophylaxis with G-CSF will be required for all subsequent cycles if one of the following criteria is applicable:
- occurrence of febrile neutropenia or infection in neutropenia at any time or;
- occurrence of NCI-CTC Grade 4 neutropenia or; delay of one therapy cycle because of leukopenia or neutropenia by more than 3 days.

6.6.5.2 mFOLFOX6

mFOLFOX6 treatment will comprise the following:

- Oxaliplatin (85 mg/m², IV infusion, Q2W)
- 5-FU (400 mg/m², bolus IV infusion followed by 2400 mg/m² continuous IV infusion, Q2W)
- Leucovorin (400 mg/m², IV infusion, Q2W) or levoleucovorin (200 mg/m², IV infusion, Q2W)

Refer to Table 12 for dose modification criteria for mFOLFOX6.

Table 12 Recommended Dose Modification Guidelines for mFOLFOX6 Drug-related Adverse Events

Category	Toxicity Gra	de	Oxaliplatin ^a	5-FU
	Neutropenia ^a	3-4	Hold until neutrophil count resolves to ≥1,500/mm ³ Reduction from 85 mg/m ² to 75 mg/m ²	Hold until neutrophil count resolves to >1500/mm³ Reduce by 20% (consider G-CSF)
Hematological	Febrile neutropenia ^a	3-4	Hold until neutrophil count resolves to ≥1,500/mm ³ Reduction from 85 mg/m ² to 75 mg/m ²	Hold until neutrophil count resolves to >1500mm ³ Reduce by 20% (consider G-CSF)
	Thrombocytopenia ^b	3-4	Hold until platelet count resolves to > 75 000/mm ³ . Reduction from 85 mg/m ² to 75 mg/m ²	Hold until platelet count resolves to >75 000/mm ³ . Reduce by 20%

PRODUCT: MK-7902 PROTOCOL/AMENDMENT NO.: 015-08

Category	Toxicity Grade	Oxaliplatin ^a	5-FU
	Persistent ^c Grade 1 or 2 neurotoxicity	Reduction from 85 mg/m ² to 75 mg/m ²	No change
	Transient ^c Grade 3 neurotoxicity	Reduction from 85 mg/m ² to 75 mg/m ²	No change
Neurotoxicity	Persistent ^c ≥ Grade 3 neurotoxicity OR any Grade 4 neurotoxicity	Discontinue	No change
	PRES/RPLS	Discontinue p	ermanently
	Bilirubin 1 to 2 x ULN	No change	Caution
	Bilirubin >2 to 4 x ULN AND/OR AST/ALT 2.5 to 5 x ULN	No change	Caution
Hepatic Impairment	Bilirubin >4 x ULN AND/OR AST/ALT 5 x ULN	No data available	OMIT if bilirubin >4 x ULN (Leucovorin to be omitted if 5-FU omitted)
	Bilirubin ANY OR AST/ALT >5 x ULN	No data available OMIT if bilirub ULN (Leucovorin to be	OMIT if bilirubin >4 x
	Creatinine clearance: 50 to 80 mL/min	No change	No change
Renal Impairment	Creatinine clearance: 30 to <50 mL/min	Caution, consider dose reduction	No change; monitor
	Creatinine clearance: <30 mL/min	Discontinue	Consider dose reduction
Other	≥ Grade 3 GI toxicity (after prophylaxis)	Hold until resolves to Grade 0-1 Reduction from 85 mg/m² to 75 mg/m² c	Hold until resolves to Grade 0-1 Reduce by 20% ^c
	Sepsis/septic shock	Discontinue	Discontinue
Hemolytic uremic syndrome OR any signs of microangiopathic hemolytic anemia		Discontinue permanently	
	Other \geq Grade 3 related organ toxicity ^d	Reduction from 85 mg/m ² to 75 mg/m ²	Reduce by 20%

PROTOCOL/AMENDMENT NO.: 015-08

Category	Toxicity Grade	Oxaliplatin ^a	5-FU
----------	----------------	--------------------------	-------------

5-FU=fluorouracil; ALT=alanine aminotransferase; AST=aspartate aminotransferase; RPLS=reversible posterior leukoencephalopathy syndrome; ULN=upper limit of normal

Further dose reduction may be considered on Sponsor's approval.

Do not retreat until the ANC \ge 1.5 x 10⁹/L and the platelets \ge 75-100 x 10⁹/L, GI and neurotoxicities have resolved and other nonhematologic toxicities \le Grade 1.

- a May consider restarting when neutrophil count resolves to ≥1000/mm³ per local guidance.
- b Discontinue if sepsis/septic shock.
- c Transient ≥7days-<1 cycle; persistent ≥1 cycle.
- d For skin toxicity, reduce 5-FU dose only.

For participants in the lenvatinib plus pembrolizumab plus chemotherapy arm: if chemotherapy (CAPOX/mFOLFOX6) is interrupted due to adverse events, the participants may extend the Induction Phase for a maximum of 6 weeks on approval by the Sponsor. The participant should not exceed 4 cycles of CAPOX treatment, or 6 cycles of mFOLFOX6 treatment.

6.6.6 Second Course

Note: As of Amendment 8, Second Course will no longer be offered. Any participant currently receiving Second Course retreatment will be able to continue treatment as planned. Imaging will be performed per local standard of care. Participants who either complete 18 cycles of pembrolizumab or discontinue pembrolizumab will be discontinued from the study following the Safety Follow-up visit. AE, SAE, and other reportable safety events will be reported and followed as described under Section 8.4. All participants in Efficacy Follow-up prior to initiation of Amendment 8 will stop efficacy assessments and be discontinued from the study. All participants in Survival Follow-up are considered to have completed the study and should have a final survival contact; these participants will no longer be contacted for survival information.

Participants who stop study intervention with SD or better and have radiographic disease progression verified by a BICR, may be eligible for up to an additional 9 cycles (approximately 1 year) of pembrolizumab treatment if they progress after stopping study intervention from the initial treatment phase.

This retreatment is termed the Second Course. Participants must provide new documented informed consent using the most recent IRB-approved version of the main consent form prior to starting the Second Course. All participants who receive the Second Course must be given pembrolizumab. In addition, participants who did not discontinue lenvatinib in the First Course (due to lenvatinib-related AEs) may begin the Second Course with lenvatinib at the highest tolerable dose received during the Consolidation Phase, per investigator's decision.

The Second Course phase of this study is only available if the study remains open and the participant meets the following conditions:

Either

- Stopped initial study intervention after attaining an investigator-determined confirmed CR based on RECIST 1.1, and
- Was treated with at least 4 cycles of pembrolizumab before discontinuing treatment, and
- Received at least 1 treatment with pembrolizumab beyond the date when the initial CR was declared

OR

• Had SD, PR, or CR and stopped study intervention after completion of 18 administrations (approximately 2 years) of study intervention for reasons other than disease progression or intolerability

AND

- Experienced an investigator-determined radiographic disease progression by RECIST
 1.1 after stopping initial treatment, and
- On unblinding at the time of centrally verified disease progression were found to have received pembrolizumab, and
- No new anticancer treatment was administered after the last dose of study intervention, and
- The participant meets all of the safety parameters listed in the inclusion criteria and none of the safety parameters listed in the exclusion criteria, and
- The study is ongoing.

An objective response or disease progression that occurs during the Second Course phase for a participant will not be counted as an event for the primary analysis of either endpoint in this study.

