CAPOX=capecitabine + oxaliplatin; DOR = duration of response; ECOG=Eastern Cooperative Oncology Group; mFOLFOX6=folinic acid, fluorouracil, and oxaliplatin; HER-2=human epidermal growth factor receptor 2; ORR = objective response rate; OS=overall survival; PFS=progression-free survival; po=per oral; qd=once daily; QW6=dosing every 6 weeks.

a. HER-2 positive participants are excluded.

Note: After the last cycle of the Induction Phase, lenvatinib will be maintained at the current dose until the start of the Consolidation Phase. The Consolidation Phase, will begin 3 weeks after the last dose of oxaliplatin induction for CAPOX and 3 weeks after C2D29 of mFOLFOX6, when the dose will be escalated to 20 mg in participants who tolerated 8 mg. Participants who have had lenvatinib-related dose reductions during induction for hematologic toxicity will have dose escalation per Table 7.

Figure 3 Second Course Treatment Phase

IV=intravenous; po=orally; Q6W=dosing every 6 weeks; qd=once daily.

Second Course is for eligible participants in both Part 1 and Part 2.

- a. Second Course is up to 9 cycles of pembrolizumab (approximately 1 year), or meeting discontinuation criteria are listed in Section 7.1. Lenvatinib may continue beyond a year, per investigator's discretion.
- b. Lenvatinib administration in the Second Course is at the discretion of the investigator. Lenvatinib may be restarted if the participant did not discontinue lenvatinib in the First Course due to lenvatinib-related AEs (Section 7.1). Lenvatinib will continue until meeting at least 1 of the discontinuation criteria listed in Section 7.1. Participants may begin the Second Course with lenvatinib at the highest tolerable dose received during the Consolidation Phase, per investigator's decision.

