									1 of the DC criteria listed in
									Section 7.1.
									Dose for lenvatinib at Second
									Course should not exceed the
									last tolerable dose during the
									Consolidation Phase.
Lenvatinib administration	<			>					Lenvatinib 20 mg orally qd.
									Pembrolizumab 400 mg IV
									Q6W.
Pembrolizumab	X	X	X						Participants who are eligible for
administration	^	Λ	Λ						SC may receive up to an
									additional 9 cycles of treatment
									with pembrolizumab.

							Posttreatment		Notes
Trial Period		_	Treatment		ЕОТ	Safety		Survival	
		(Cycle =6 weeks			Follow-	ru b	Follow-	
		I		1		up ^a	Follow-up ^b	up	·
Visit Timing/	40			>9	At	30 Days After		Every	All procedures are to be performed before
Cycle Number	1 ^c	2	3 to 9	(lenvatinib	DC	Last	Every	12	administration of study
				only)		Dose	12 weeks	weeks	intervention unless otherwise
Scheduling Window (days)	+3	±3	±3	±3		+7	±7	±14	indicated
Efficacy Procedures			T	1	T			1	
Tumor imaging									SC baseline imaging should be performed within 28 days before SC C1. Perform imaging Q12W (84 ± 7 days) from SC C1. Schedule should be followed regardless of treatment delays. -If imaging was obtained within 4 weeks before DC, scan at DC is not mandatory. *Follow-up visits may be scheduled to coincide with Follow-up imaging. As of Amendment 8 on-study imaging is no longer required and should be performed per local standard of care.
Subsequent antineoplastic therapy status					X	X	X	X	All anticancer therapy will be recorded until time of death or termination of survival follow-up. If a clinic visit is not feasible, follow-up information may be obtained via telephone or email.
Survival status		<		>	X	Participants may be contacted for survival status at any time during the course of the study.			

							Posttreatment		Notes
Trial Period		(Treatment Cycle =6 weeks		EOT	Safety Follow- up ^a	Follow-up ^b	Survival Follow- up	
Visit Timing/ Cycle Number	1°	2	3 to 9	>9 (lenvatinib only)	At DC	30 Days After Last Dose	Every 12 weeks	Every 12 weeks	All procedures are to be performed before administration of study intervention unless otherwise
Scheduling Window (days)		±3	±3	±3		+7	±7	±14	indicated
Clinical Procedures/Assessm	nents		1	, ,		1			
									Will be assessed on Day 1 and Day 22 of every cycle. Report AEs occurring within 30 days after the last dose of study intervention.

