Note: As of Amendment 8, participants who either completed lenvatinib plus pembrolizumab or chemotherapy administration or discontinued lenvatinib plus pembrolizumab or chemotherapy will discontinue from the study following the Safety Follow-up visit (Section 8.11.5.1). AE, SAE, and other reportable safety events will be reported and followed as described under Section 8.4. All participants in Efficacy Follow-up prior to initiation of Amendment 8 will stop efficacy assessments and be discontinued from the study and should continue with tumor imaging per local standard of care. All participants in Survival Follow-up prior to initiation of Amendment 8 are considered to have completed the study and should have a final survival contact; these participants will no longer be contacted for survival information.

PRODUCT: MK-7902 PROTOCOL/AMENDMENT NO.: 015-08

Specific procedures to be performed during the study, including prescribed times and associated visit windows, are outlined in Section 1.3 of the SoA. Details of each procedure are provided in Section 8.

The study design is depicted in Figure 1 (Safety Run-in), Figure 2 (Main Study) and Figure 3 (Second Course Treatment Phase).

In Part 2, this study will use a group sequential design, using an eDMC to monitor safety and efficacy during the course of the study.

Participants treated with pembrolizumab who complete 18 cycles (2 years) of treatment with SD or better, or participants who attain an investigator-determined CR and have received at least 4 cycles of pembrolizumab may be eligible for retreatment with up to an additional 9 cycles (approximately 1 year) of pembrolizumab if they experience radiographic disease progression confirmed by BICR after stopping treatment in the initial treatment phase. This retreatment is termed the Second Course Treatment Phase and is only available if the study remains open and the participant meets the criteria specified in Section 7.1. The decision of whether to continue lenvatinib treatment during the Second Course Treatment Phase will be at the discretion of the investigator. If continued, participants will be retreated at the same dose level and frequency as when they last received the combination of lenvatinib plus pembrolizumab. **Note: As of Amendment 8, Second Course will no longer be offered**. Any participant receiving Second Course retreatment prior to the initiation of Amendment 8 will be able to continue treatment as planned.

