In an open-label Phase 1b/2 study of lenvatinib plus pembrolizumab in participants with advanced gastric cancer many patients were treated with the combination therapy at 20 mg daily dose of lenvatinib. TRAE led to dose interruptions in 28 patients (97%) and at least 1 dose reduction of lenvatinib in 29 patients (100%); 1 level dose reduction (14 mg) in 9 patients (31%), 2 level (10 mg) in 14 patients (48%), 3 level (8 mg) in 5 patients (17%) and 4 level (4 mg) in 1 patient (3%) [Kawazoe, A., et al 2020a]. As described in the background, noninferiority of lower dose lenvatinib has been studied in approved indications of DTC and RCC, showing that lower dosages of lenvatinib have failed to show noninferiority to higher approved dosing. These studies suggest that maximizing the dose of lenvatinib may be important for best long-term outcomes [Brose, M. S., et al 2020] [Pal, S., et al 2020]. Based on these data, during Consolidation Phase, the starting dose of lenvatinib will be 20 mg oral daily combined with pembrolizumab 400 mg every 6 weeks. Dose escalation schema in this study is defined such that only patients who tolerate 8-mg dose during induction would be eligible to escalate the lenvatinib dose. We expect that some participants will subsequently

need dose reduction due to toxicity but understand that maximizing the lenvatinib the dose may confer better long-term outcomes.

A 21-day Safety Run-in in Part 1 will include approximately 12 participants, and these participants will start on an 8 mg dose of lenvatinib (see Section 4.1 for details). For those participants who do not tolerate 8 mg during the Induction Phase or 20 mg during the Consolidation Phase due to severe hypersensitivity and/or Grade 3 or higher ongoing AEs, dose reduction/discontinuation/dose escalation/dose reescalation will occur as described in detail in Section 6.6.3.

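### The Second Course schedule gives lenvatinib as a flat 20 mg daily next to a ceiling at the last tolerable Consolidation dose, and two other wordings elsewhere are not reconciled with it

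*Combined protocol and SAP*

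**What the plan says.** Four places in the current text state the lenvatinib dose for Second Course.

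- **Section 1.3.5, administration row:** "Lenvatinib 20 mg orally qd".
- **Section 1.3.5, dispensing row, directly above:** the dose is not to exceed the "last tolerable dose during the" Consolidation Phase.
- **Section 6.6.6:** participants who did not stop lenvatinib for related adverse events "may begin the Second Course with lenvatinib at the highest tolerable dose received during the Consolidation Phase", as the investigator decides. Note b to Figure 3 (Section 1.2) has the same rule: "Participants may begin the Second Course with lenvatinib at the highest tolerable dose received during the Consolidation Phase, per investigator's decision".
- **Section 4.1:** if lenvatinib is continued, "participants will be retreated at the same dose level and frequency as when they last received the combination of lenvatinib plus pembrolizumab".

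Amendment 8 ended new Second Course entry but did not stop treatment already under way. Section 6.6.6 says: "Any participant currently receiving Second Course retreatment will be able to continue treatment as planned". Section 4.1 says: "Any participant receiving Second Course retreatment prior to the initiation of Amendment 8 will be able to continue treatment as planned". The note at the head of Section 1.3.5 states that the schedule was cut down to the assessments still required. Both dose rows survived that edit.

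**The concern.** A site with a continuing Second Course participant who was reduced during Consolidation finds two incompatible entries in adjacent rows of one table. Nothing visible in the schedule labels 20 mg as a nominal or starting dose.

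The first consequence is for dosing: two sites could give different doses and each cite the protocol. The second is for safety reporting. Section 8.5 defines lenvatinib overdose by reference to the dose the protocol prescribes, when an adverse event accompanies it. It requires a report within 24 hours, and Section 8.4.7 makes such an overdose an event of clinical interest. For a reduced participant who takes 20 mg and has an adverse event, whether that report is due depends on which row is read as the prescription. Section 9.11, which calls for deviations from protocol-directed dosing to be reported, has the same dependence.

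**Working it through.** There is no statistical figure to reproduce. The check is a comparison of the wordings, applied to three dose histories. The histories are illustrative; their dose levels (20, 14, 10, 8 mg) are those reported for the gastric phase 2 study in Section 4.3.2, because this trial's own lenvatinib tables are redacted.

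| History | 1.3.5 administration row | 1.3.5 dispensing row (ceiling) | 6.6.6 and Figure 3 note | 4.1 |
|---|---|---|---|---|
| A. 20 mg tolerated throughout | 20 | 20 | 20 | 20 |
| B. Reduced 20 to 14 to 10 mg for intolerance; combination ends at 10 mg | 20 | 10 | 10, as the higher levels were not tolerated | 10 |
| C. 20 mg tolerated for some cycles, 10 mg at the end of the combination, 8 mg on lenvatinib alone after pembrolizumab ended | 20 | 8 if the lenvatinib-only period counts as Consolidation, otherwise 10 | 20 or 10, depending on how highest tolerable is read | 10 |

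1. In A all wordings agree.
2. In B there are two values. The flat entry exceeds the ceiling by 20 − 10 = 10 mg, and the other three wordings coincide.
3. In C the other wordings can separate as well. C is possible because Section 8.11.3 sets no limit on lenvatinib duration, so the last dose with the combination need not be the last lenvatinib dose.
4. Sections 4.1 and 6.6.6 also differ in force: the first prescribes, the second permits at the investigator's discretion.

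How often a last tolerable dose below 20 mg would arise is not stated for this trial. Section 4.3.2 gives the phase 2 counts by level reached: 9 (14 mg), 14 (10 mg), 5 (8 mg) and 1 (4 mg). These sum to 9 + 14 + 5 + 1 = 29, which is all 29 patients.

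**The case against.** The wordings are not all the same kind of rule. The dispensing row sets a ceiling and prescribes nothing. Sections 4.1 and 6.6.6 and the Figure 3 note are mainly restart rules, and restarts have ended. The 20 mg entry may be nominal: the chemotherapy rows of the other schedules also list flat doses although Tables 10 to 12 allow reductions. Parts of Section 6.6.3 are redacted and may hold a clarifying rule.

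Most of this stands and narrows the point to the two schedule rows. It does not remove it. A nominal reading is plausible but is not stated, and a hidden rule would still leave the visible rows in conflict.

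Three stronger readings are not supported.

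- **Every reduced participant faces four different doses.** History B shows two values, not four.
- **Essentially every Second Course participant is affected.** This carries 29 of 29 over from a study in which lenvatinib started at 20 mg. Here only those who tolerate 8 mg in induction escalate. Entry to Second Course required a confirmed complete response or 18 completed administrations, and lenvatinib only where it had not been stopped for related adverse events. Section 4.3.2 also reports reduction and/or interruption, taken together, in 85% of patients in a solid-tumour study of the combination.
- **Deviations cannot be defined at all.** The ambiguity concerns reduced participants in a subgroup now closed to entry.

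**Conclusion.** The contradiction within Section 1.3.5 is real and is in current text. It affects any continuing participant whose last tolerable Consolidation dose was below 20 mg. The differences from Sections 1.2, 4.1 and 6.6.6 are secondary: they often vanish after stepwise reductions and reappear in histories such as C.

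The reach is limited. The documents do not say how many participants remain in Second Course, and the number may be small or zero. Response and progression in Second Course are excluded from PFS, OR and DOR (Section 9.6.1), and the primary safety analyses take only events before Second Course (Section 9.6.2.1). The point therefore concerns dosing conduct and safety reporting, not those analyses. The phase 2 counts support only the statement that reductions from 20 mg are likely to be common. The conclusion assumes that no redacted text in Section 6.6.3 settles which entry governs. It is a minor point, but relevant to safety.

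**What to change.** Reconcile the Figure 3 note in Section 1.2, both lenvatinib rows in Section 1.3.5, Section 4.1 and Section 6.6.6 into one instruction for participants continuing Second Course, and remove or cross-refer the other wordings. That instruction should serve as the prescribed dose for Sections 8.5 and 9.11. The choice of rule is for the sponsor; none is proposed here.

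The cost is a short clarification of retained text. If nobody remains in Second Course, the sponsor can confirm that and close the point.
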